## 2.2 Secondary Endpoints

Secondary endpoints include the following:

1. **Requirement for invasive mechanical ventilation for > 48 hours**  
Invasive mechanical ventilation (MV) for > 48 hours within 7 days from PSHA
2. **Requirement for respiratory support for > 48 hours**
  - Requirement for non-invasive ventilation (NI V) above patient's baseline requirement after hour 48 from PSHA, or continuous positive airway pressure (CPAP) above patient's baseline requirement, not related to obstructive sleep apnea (OSA), for > 48 hours within 7 days from PSHA
  - Requirement for O2 therapy > 40 % FiO2 or > 5 LPM via nasal cannula (and above patient's baseline), for > 48 hours within 7 days from PSHA
3. **ICU Length of Stay**  
ICU length of stay, during initial PSHA, will be determined by calculating the number of days/hours spent in ICU. The following will be documented:
  - Time of initial admission to the ICU to actual time of initial discharge from the ICU
  - Total ICU days/hours (includes readmissions), during the initial hospital stay
4. **Hospital Length of Stay (LOS)**  
Hospital length of stay will be determined by calculating the number of days/hours spent in hospital. LOS will be calculated for initial and total hospital stays. The following will be documented:

- Time of admission to time of discharge from the hospital (total days/hours), for each hospital admission.

#### **5. Time on Mechanical Ventilation**

Time on mechanical ventilation, during the initial hospital stay, will be documented as follows:

- Time to initial extubation
- Total time on invasive mechanical ventilation - will be determined for each patient by calculating the total number of days/hours intubated and mechanically ventilated from the time of PSHA until the time of initial hospital discharge.
- Total time on non-invasive ventilation - will be determined for each patient by calculating the total number of days/hours ordered for non-invasive ventilation from the time of PSHA until the time of initial hospital discharge.

#### **6. Readmission to ICU and transfers to elevated level of care for pulmonary complications**

Readmissions to ICU and transfers to an elevated level of care, during the initial hospital stay, will be documented for each event. The following will be documented:

- Number of readmissions to ICU or elevated level of care events
- Number of patients requiring readmission to the ICU or to an elevated level of care

#### **7. Readmission to Hospital**

Hospital records will be reviewed at each site, 30 days after the last patient has been discharged from the hospital. Readmissions, for any cause, within 30 day of hospital discharge for any study patient will be documented.

### **3 STUDY DESIGN**

This is a non-randomized facility level pre-post intervention study conducted in two stages for the primary purpose of evaluating the effect of The MetaNeb® System on postoperative pulmonary complications in high risk patients undergoing thoracic and abdominal surgeries. The study will be conducted in two to four (2-4) tertiary academic medical facilities in the US that have not previously used The MetaNeb® System in post-thoracic, post-aortic, or post-upper abdominal surgery patients. After assessing outcomes during a baseline period, therapy with The MetaNeb® System will be introduced and incorporated into the respiratory care treatment regimens and outcomes will be assessed after the change in practice.

#### **Stage I**

In Stage I of the study, a retrospective review of medical records for post-surgical patients, who received STANDARD THERAPY as defined by current hospital and Respiratory Care department policies and procedures. This will be a retrospective data collection only. Respiratory Care therapies (e.g. nebulizer treatments, chest physiotherapy, etc.) that were

delivered during the first seven (7) days following surgery, including delivered frequency, will be collected.

The purpose of study Stage I is to estimate the incidence of postoperative pulmonary complications in post-surgical patients receiving standard of care per hospital and Respiratory Care department procedures and policies. Data collected in Stage I will include data from the medical records of 200 randomly selected, eligible patients treated during the year prior to the CHANGE IN PRACTICE.

#### Stage II

In Stage II, a CHANGE IN PRACTICE will be made and patients will receive the routine standard care prescribed by the patient's health care team with the addition of therapy with The MetaNeb® System. With the exception of standard airway clearance and lung expansion procedures, other components of the patients respiratory care regimen will remain the same as during the standard therapy period, however the CHANGE IN PRACTICE will incorporate the use/treatment with The MetaNeb® System as an alternative to usual airway clearance and lung expansion procedures. Use of The MetaNeb® System will follow the labeling of the device. During Stage II, data from approximately 200 patients will be collected from the medical records across the sites. Respiratory Care therapies, including therapy with The MetaNeb® System, that are delivered during the first seven (7) days post-surgery hospital admission in Stage II, including delivered frequency, will be collected.

Exceptions to the above treatment protocols required for patient care as determined by the treating physician will be collected

#### **4 Study Activities**

Table 1. Study Observation Table:

Day	Pre-Surgery	Day of Surgery	Post Surgery Day 1 - Day 7	Hospital Discharge	Early Term	Day 30 Post Discharge
Selection Criteria / Enrollment	X					
Informed Consent *	X					
Demographic Data	X					
Medical History	X					
Pre-Surgery Respiratory Status (Patient's Baseline)	X					
Post-Surgical Data (day 0) at day of surgery.		X				
Location (7A & 7P)		X	X			
Respiratory Status (Each Shift)		X	X			
Respiratory Milestones	X		X			
Respiratory Treatments		X	X			
Hospital Discharge Summary				X		
ICU Admission/Discharge Summary (Day 8 - Discharge)				X		
Discharge Respiratory Summary (Day 8 - Discharge)				X		
30-day Readmission						X
Study Exit Form					X	X

## 5 SAMPLE SIZE JUSTIFICATION

No formal sample size determination was performed for this study.

## 6 STATISTICAL ANALYSIS METHODS

The statistical software, SAS®, will be used for all summaries and statistical analyses.

Summary statistics will be used throughout. For continuous endpoints, the summary statistics will generally include: number of subjects with data (n), mean, standard deviation (SD), median, and range (Min, Max). For categorical endpoints, the summary statistics will generally include: number of subjects randomized and dosed, number with data, and the percentage of those with data in each category.

All statistical tests will be 2-sided with a type I error rate of 5%, unless otherwise specified.

### 6.1 Description of Analytical Methods

#### 6.1.1 Derived Variables

**Primary Endpoint:** occurrence of a postoperative pulmonary complication (PPC).

Stage I: during the 7 days post-surgery hospital admission (PSHA)

Stage II: during the 7 days PSHA. Event must occur after MetaNeb® administration.

For each subject, occurrence of a PPC will be set to yes if one or more of the four conditions below occur.

- i. **PPCflg1:** Patient Requires Prolonged Mechanical Ventilation beyond Hour 24 from PSHA.

Duration of invasive mechanical ventilation (IMV) is defined as IMV stop time minus IMV start time where:

IMV Start Time=date & time of the later of start of IMV or PSHA

IMV Stop Time=date & time of the earlier of stop of IMV or PSHA+7

If IMV is required on more than one occasion during the 7 days following PSHA, then the cumulative sum will be calculated.

$$\text{PPCflg1} = \begin{cases} 1 & \text{if the latest IMV stop time is more than 24 hours after PSHA} \\ 0 & \text{otherwise} \end{cases}$$

If IMV start date is available, but the start time is missing, then a clock time consistent with the earliest possible time of the day will be imputed, ex. Hour 00.00 or PSHA clock time.

If the IMV stop date is available, but the stop time is missing, then the IMV stop time will be taken as the assessment time.

- ii. **PPCflg2:** Patient Requires Prolonged Respiratory Support beyond Hour 24 from PSHA

- a) Duration of non-invasive MV (NIMV) is defined as NIMV Stop time minus NIMV start time. NIMV start and stop times are defined similarly to those of IMV.

Imputations for missing NIMV start or stop times will be used similarly to those of IMV.

- b) Duration of CPAP is defined as CPAP Stop time minus CPAP Start time.

- c) Duration of O2 therapy [if >40% FiO2 or >5 LPM via Nasal Cannula] will be calculated similarly.

Duration of respiratory support is defined as the sum of durations of NIMV, CPAP, and O2 therapy during the 7 days following hospital admission.

$$\text{PPCflg2} = \begin{cases} 1 & \text{if the latest NIMV, CPAP, or O2 therapy stop time} \\ & \text{is more than 24 hours after PSHA} \\ 0 & \text{otherwise} \end{cases}$$

- iii. **PPCflg3:** Diagnosis of pneumonia

- iv. **PPCflg4:** Readmission to ICU (or transfer to an elevated care) for PPC with 7 days of PSHA

Secondary Endpoints derivations will follow similar logic as that of the primary endpoint, when calculating incidence of PPC > 48 hours. For time to initial extubation, if extubation occurred prior to hospital admission, then time to initial extubation will be set to zero.

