3.3 Evaluation Criteria/Effectiveness

The CHANGE IN PRACTICE therapy regimen (which includes therapy with The MetaNeb® System) will be evaluated to determine if there is a decrease in the number of patients who experience Significant Postoperative Pulmonary Complications among the group of patients treated with The MetaNeb® System. Endpoints are described below:

Primary Endpoint:

Significant Postoperative Pulmonary Complication (PPC):

One or more of the following that occurs within seven (7) days of the post-surgical admission will be considered a Significant Postoperative Pulmonary Complication (PPC)

- **Patient Requires Prolonged Mechanical Ventilation:**

Defined as patient requirement for invasive mechanical ventilation (MV) for > 24 hours (after hour 24) post-operatively. This includes patients that require re-intubation and MV after hour 24, regardless of length of time on MV in the first 24 hours postoperatively.

Hill-Rom®	Evaluation of a practice change to include The MetaNeb® System to reduce postoperative pulmonary complications	Page 17 of 31
CBI	8 September 2016	Rev C Protocol #: CR-RR2015-001

- **Patient requires prolonged respiratory support for > 24 hours from post-surgical admission**
 - Requirement for non-invasive ventilation (NIV) above patient's baseline requirement after hour 24, or continuous positive airway pressure (CPAP) above patient's baseline requirement after hour 24.
 - Requirement for O₂ therapy > 40 % FiO₂ or > 5 LPM via NC (and above patient's baseline) after hour 24 postoperatively.
- **Diagnosis of Pneumonia Within Seven (7) Days**
 - Physician documented pneumonia AND
 - Radiologists report indicating pneumonia / new or expanded infiltrate AND
 - Elevated or low Temperature (> 38° C or < 36° C, or as defined by the site) and/or elevated white count above the upper level of normal as defined by the site
- **Readmission to ICU (or transfer to an elevated level of care) for pulmonary complications within seven (7) days of the post-surgical hospital admission**

Defined as readmission to the ICU within seven days of post-surgical hospital admission or readmission to an elevated care unit such as special care or ICU step-down unit after being moved to a lower (e.g. general care) floor (e.g. patient discharged from ICU on day 4 at 0800 is readmitted to the ICU before day 8 at 0800).

Secondary Endpoints:

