Respiratory Treatments: Standard respiratory treatments including CPAP therapy (non-continuous), IPPB, Nebulizer treatments, Chest physiotherapy, and others will be

Hill-Rom®	Evaluation of a practice change to include The MetaNeb® System to reduce postoperative pulmonary complications			Page 21 of 31
	CBI	8 September 2016	Rev C	Protocol #: CR-RR2015-001

recorded for each day until discharge from the hospital, or through day seven (7) following the day of surgery, whichever occurs first. Type of therapy and the number of treatments received on each day will be recorded.

During Stage II, each MetaNeb® therapy will be documented including time and duration of therapy and adherence to defined treatment regimen

Hospital Discharge Summary: A summary including date and time of discharge along with the location to which the patient is being discharged will be completed after discharge.

ICU Admission/Discharge Summary (Day 8 – Discharge): Dates and times of all ICU admissions, or admissions to a unit for an elevated level of care, along with discharges from those units, that occur between post-surgery day 8 and discharge from the hospital, will be documented.

Discharge Respiratory Summary (Day 8 – Discharge): Dates and times of each initiation and discontinuation of mechanical ventilation that occur between post-surgery day 8 and discharge from the hospital, will be documented.

30-day Readmission: Hospital medical records for each patient will be evaluated after 30 days post discharge, to determine if any hospital readmissions had occurred.

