The secondary endpoints as listed in section 3.3 will be summarized with descriptive summary statistics appropriate for continuous or categorical data, depending on the outcome being summarized:

1. Requirement for invasive mechanical ventilation for more than 48 hours.
2. Requirement for respiratory support for more than 48 hours
3. Length of ICU stay (ILOS)
4. Length of hospital stay (HLOS)
5. Time on mechanical ventilation
6. Readmission to ICU
7. Readmission to hospital

Hill-Rom®	Evaluation of a practice change to include The MetaNeb® System to reduce postoperative pulmonary complications	Page 23 of 31
CBI	8 September 2016	Rev C

Stage I and Stage II results will be compared for the purpose of identifying any statistical associations that can be attributed to use of The MetaNeb® System.

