## 2 STUDY OBJECTIVES AND ENDPOINTS

### 2.1 Primary Objective and Endpoint

The primary objective of Stage I of this study is to estimate the incidence of postoperative pulmonary complications (PPC) in post-surgical patients receiving standard of care per hospital and respiratory care department procedures and policies.

The primary objective of Stage II of this study is to estimate the incidence of PPC in post-surgical patients receiving change in practice therapy regimen, which includes the addition of the MetaNeb® System to the standard of care per hospital and respiratory care department procedures and policies.

The primary endpoint at each stage is to evaluate the proportion of subjects who experience a significant PPC within seven (7) days of: post-surgical hospital admission (Stage I) or post-surgical hospital admission and MetaNeb® System administration (Stage II). A PPC is defined as having one or more of the following:

- 1. Patient requires prolonged mechanical ventilation for > 24 hours**  
Invasive mechanical ventilation (MV) for > 24 hours from post-surgical hospital admission (PSHA)
- 2. Patient requires prolonged respiratory support for > 24 hours from PSHA**

- Requirement for non-invasive ventilation (NI V) or continuous positive airway pressure (CPAP) above patient's baseline requirement, not related to obstructive sleep apnea (OSA), for > 24 hours from PSHA
- Requirement for O2 therapy > 40 % FiO2 or > 5 LPM via NC (and above patient's baseline), for > 24 hours from PSHA

3. **Diagnosis of Pneumonia within 7 days from PSHA**
  - Physician documented pneumonia, and
  - Radiologists report indicating pneumonia / new or expanded infiltrate, and
  - Elevated or low Temperature (> 38° C or < 36° C, or as defined by the site) and/or elevated white count above the upper level of normal as defined by the site
4. **Readmission to ICU (or transfer to an elevated level of care) for pulmonary complications**  
Defined as readmission to the ICU or readmission to an elevated care unit within 7 days from PSHA

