## **6.2 Analysis Population**

Two analysis populations will be defined:

- FAS: The full analysis data set will contain all subjects, for whom hospital records were pulled and recorded.
- ITT: The intent-to-treat (ITT) population, a subset of the FAS, includes all subjects who satisfied all the inclusion criteria and none of the exclusion criteria. For Stage II of the study, patients who did not receive the MetaNeb® system will be excluded from the ITT population.

The ITT population will be the primary population for the analysis.

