### **6.3 Analysis Methods – Primary and Secondary Endpoints**

#### **Primary Endpoint— Proportion of subjects who have a postoperative pulmonary complication**

The proportion of subjects who have a PPC within 7 days of post-surgery hospital admission will be presented with 95% confidence intervals.

Incidence of each of the 4 components that contribute to the primary endpoints, will also be presented.

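### The SAP counts a Stage II pulmonary complication only if it follows MetaNeb treatment and sets no matching condition for Stage I, so the rule can lower the Stage II rate and never raise it

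*SAP*

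**What the plan says.** Protocol 3.3 defines the primary endpoint once, for both stages: "One or more of the following that occurs within seven (7) days of the post-surgical admission will be considered" a significant PPC. The definition does not refer to the time of treatment.

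SAP 6.1.1 splits it by stage. Stage I takes events in the 7 days from PSHA. Stage II takes the same window and adds a condition: "Stage II: during the 7 days PSHA. Event must occur after MetaNeb® administration". SAP 2.1 has the same split, setting the window within seven days of "post-surgical hospital admission (Stage I) or post-surgical hospital admission and MetaNeb® System administration (Stage II"). SAP 6.3 does not repeat the condition: "The proportion of subjects who have a PPC within 7 days of post-surgery hospital admission will be presented with 95% confidence intervals".

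Three other provisions bear on the point:

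- **Population.** Under SAP 6.2, in Stage II, "patients who did not receive the MetaNeb® system will be excluded from the ITT population". Treated patients stay in, whenever their treatment began.
- **Derivation.** Under SAP 6.1.1, the ventilation flag is 1 "if the latest IMV stop time is more than 24 hours after PSHA". The respiratory-support flag has the same form. Neither contains a MetaNeb time.
- **Use of the result.** Protocol 3.5.2 says that "Stage I and Stage II results will be compared for the purpose of identifying any statistical associations" attributable to the device.

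**The concern.** A comparison of two event rates needs the same event definition on both sides. Here a patient with pneumonia or an ICU readmission before the first MetaNeb treatment is an event in Stage I and a non-event in Stage II. The difference comes from the scoring rule, not from the device, and it always runs in the device's favour.

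Protocol 3.3 evaluates the change-in-practice regimen as a whole. In Stage II the other airway clearance and lung expansion therapies are not delivered, so a complication that arises before the first MetaNeb treatment still arises under that regimen. Discarding it removes part of what the study set out to measure.

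The rule also cannot be programmed as written, because the SAP does not say when a support-based event occurs. Someone would have to choose a reading later. SAP section 1 starts Stage II only after the Stage I data are analysed, so the comparator rate would be known by then. SAP 6.1.1 also derives the 48-hour secondary endpoints by similar logic, so the problem may spread to them.

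**Working it through.** The plan states no power, effect size or formal sample size (SAP 5), so it has no figure to reproduce. The check covers the direction of the effect, what determines its size, and an illustration.

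**1. Direction.** Let n be the Stage II patients analysed, x those with a PPC in the 7 days, and k those whose only qualifying events precede first treatment (0 ≤ k ≤ x ≤ n).

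- Protocol rule: x/n.
- SAP rule, patients kept in the denominator as SAP 6.2 implies: (x − k)/n ≤ x/n.
- If those patients were removed instead: (x − k)/(n − k) ≤ x/n, because n(x − k) ≤ x(n − k) reduces to x ≤ n.

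The Stage II rate falls or stays the same in every case. Enumerating all pairs (x, k) at n = 200 confirmed this. The Stage I rate is not touched.

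**2. What determines the size.** Two facts are needed, and the documents supply neither.

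- *Time of first treatment.* No latest time is given. The protocol refers to treatment procedures and a defined regimen that it does not include.
- *When a component 1 or 2 event occurs.* If it is dated at hour 24 and treatment starts earlier, these events are all kept. Only earlier pneumonia or ICU readmission is lost, and the bias may be near nil. If it is dated at the start of support, ventilation running since PSHA precedes any treatment and could be dropped. The loss could then be large.

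**3. Illustration.** Inputs from the documents:

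- about 200 patients per stage (protocol synopsis);
- PPC incidence p of 5–15% (protocol 3.5.1);
- two-sided 5% level (SAP 6).

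Assumptions:

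- no device effect;
- a share f of Stage II events discarded, from 0 to 40%;
- a pooled z-test or Fisher's exact test, since the SAP names no between-stage test.

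Expected events lost = 200 × p × f. Counted Stage II rate = p(1 − f), so the spurious relative risk is 1 − f. For example, at p = 10% and f = 20%, 200 × 0.10 × 0.20 = 4 of 20 events are lost, the counted rate is 8% and the relative risk is 0.80.

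The chance of a falsely significant benefit is the sum of Bin(x; 200, p) × Bin(y; 200, p(1 − f)) over all outcomes (x, y) where the test gives p ≤ 0.05 in favour of Stage II.

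| Stage I rate | f | Events lost | Pooled z | Fisher exact |
|---|---|---|---|---|
| 5% | 0% | 0 of 10 | 2.4% | 1.4% |
| 5% | 10% | 1 of 10 | 4.1% | 2.5% |
| 5% | 20% | 2 of 10 | 6.7% | 4.2% |
| 5% | 40% | 4 of 10 | 17.0% | 11.3% |
| 10% | 0% | 0 of 20 | 2.4% | 1.7% |
| 10% | 10% | 2 of 20 | 5.1% | 3.7% |
| 10% | 20% | 4 of 20 | 10.0% | 7.5% |
| 10% | 40% | 8 of 20 | 30.6% | 25.2% |
| 15% | 0% | 0 of 30 | 2.5% | 1.8% |
| 15% | 10% | 3 of 30 | 6.3% | 4.7% |
| 15% | 20% | 6 of 30 | 13.9% | 11.0% |
| 15% | 40% | 12 of 30 | 45.5% | 39.9% |

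The rows at f = 0 are the result after the fix.

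**The case against.** **The loss may be nil.** Protocol 3.3 and the SAP flags define components 1 and 2 by support after hour 24, so a patient ventilated from PSHA has no event before then. The observation table in both documents allows treatments to be recorded on the day of surgery. This is the more natural reading, and it favours a small loss. It does not establish one, because no latest treatment time is given and the SAP never dates these events.

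**The condition may never operate.** The PPC variable is set from four flags, and none contains a MetaNeb time. Programmed literally, the flags would count every event. That is fair, but it means that SAP 6.1.1 states a rule its own formulas do not implement, which also has to be resolved.

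**SAP 6.3 is not a contradiction.** It reports a variable derived elsewhere and need not repeat the derivation. Accepted. The conflict that counts is with protocol 3.3.

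**SAP 2.1 might move the window.** Its wording could be read as starting the 7 days at MetaNeb administration, which could admit later events. SAP 6.1.1 anchors the window to PSHA and cuts ventilation off at PSHA+7, which rules this out for the derived endpoint. The finding that the rate can never rise belongs to the 6.1.1 rule.

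**The error rates are assumption on assumption.** Neither f nor the test comes from the documents, and the SAP's primary analysis is a proportion with a confidence interval. The table shows how the error grows with the loss, not how large the loss is. The protocol still plans the comparison, and rates shown side by side carry the same bias without any test.

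**Only events after exposure can reflect the device.** That argument would need a matching starting point in Stage I, and there is none.

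**Conclusion.** The concern holds and should be fixed before the analysis. The SAP's primary endpoint departs from the protocol's and is conditioned on treatment in one stage only. Confidence in the asymmetry and its direction is high, since they follow from the text and from the inequality in step 1. Confidence in the size is low: it ranges from near nil to large, depending on treatment timing and event dating that the documents leave open. The seriousness rests on a one-directional rule in the primary endpoint and its conflict with the protocol, not on the illustrative error rates.

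The removal of untreated Stage II patients from the primary population (SAP 6.2) is a separate asymmetry. Those patients are dropped, not scored as PPC-free, and the figures here do not include them.

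**What to change.** - In SAP 6.1.1, delete the sentence requiring a Stage II event to follow MetaNeb administration. In SAP 2.1, delete the reference to device administration from the Stage II window.
- State that every qualifying event from PSHA to PSHA+7 days is scored identically in both stages, as in protocol 3.3, and that the 48-hour secondary endpoints follow the same rule.
- If events after first treatment are of interest, report them for Stage II as a labelled supportive summary. For that summary, define when a component 1 or 2 event occurs: for example, at PSHA+24 hours if support is in place then, otherwise at the start of the later episode.

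A common landmark applied to both stages would also restore symmetry, but it would depart from the protocol endpoint.

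The cost is SAP wording only. The supportive summary needs no new data, because under protocol 3.4.1 "each MetaNeb® therapy will be documented including time and duration of therapy and adherence to defined treatment regimen". The downside for the sponsor is that the Stage II rate may look slightly less favourable. This change does not remove the SAP 6.2 exclusion, which needs its own correction.

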Number of Subjects:	The sample size will be approximately 400 patients, 200 in the retrospective STANDARD THERAPY group and 200 in the prospective CHANGE IN PRACTICE group.		
Study Population:	The study population consists of adult post-surgical patients who have undergone thoracic, aortic or upper abdominal surgery who are at high risk for PPCs.		
Inclusion/Exclusion Criteria:	
Inclusion Criteria:
 
Patients who meet all of the following criteria will be included in the study:
 
• Age \geq 18 years• Post-thoracic, -upper abdominal or -aortic surgery• Open surgical procedure• Incision at or above the umbilicus• High risk defined by:
• Documented ASA class \geq 3 
OR
 
• Documented ASA class 2 AND One or more of the following:
• Current smoker or smoking history within past 6 months• History of COPD• Documented obesity and/or BMI \geq 30 kg/m²• Age \geq 75 
Exclusion Criteria:
 
Patients who meet any of the following criteria will be excluded (or will be exited) from the study:
 
• Contraindication to Continuous High Frequency Oscillation (CHFO) therapy (e.g. untreated tension pneumothorax)• Minimally invasive, or “... scopic” procedure.• Spinal surgery involving a posterior approach• Surgery for organ transplant• Chronic invasive positive pressure ventilation (PPV)		

Statistical Methods:	
Descriptive summary statistics will be provided for demographics, the primary and secondary endpoints. Continuous data will be summarized with N, mean, median, standard deviation, min, and max. Categorical data will be summarized with the number and percent of patients in each category. Time to event data (ex. Time to readmission) will be summarized with methods appropriate for survival data including a Kaplan-Meier plot.
 
Ninety-five percent (95%) confidence interval will be computed for the primary endpoint, the incidence of significant postoperative pulmonary complications. Incidence rates for various demographic subsets, surgery types, and different population subsets may be presented as outlined in the statistical analysis plan document, to be published prior to study completion. Stage I and Stage II incident rates will be compared for the purpose of identifying any statistical associations that can be attributed to use of The MetaNeb® System.
		

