#### **Secondary Efficacy Endpoints**

Proportions of subjects will be presented for the following endpoints:

1. Requirement for invasive mechanical ventilation beyond Hour 48 from PSHA
2. Requirement for respiratory support beyond Hour 48 from PSHA
3. Readmissions to ICU and transfers to an elevated level of care within 7 days of PSHA during the initial hospital stay
4. Readmissions to ICU and transfers to an elevated level of care during the initial hospital stay
5. Readmissions to hospital after PSHA discharge

Mean, median, and standard deviation will be presented for the following endpoints:

1. ICU Length of Stay
2. Hospital Length of Stay
3. Time on mechanical ventilation
4. Time to extubation

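### The SAP has no rule for death: on the natural reading an early death on the ventilator scores better than a survivor extubated at hour 26, and no planned table counts deaths

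*SAP*

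**What the plan says.** **Primary endpoint (SAP 6.1.1).** The composite rule is "For each subject, occurrence of a PPC will be set to yes if one or more of the four conditions below occur". PPCflg1 is 1 "if the latest IMV stop time is more than 24 hours after PSHA" and 0 otherwise. PPCflg2 is 1 "if the latest NIMV, CPAP, or O2 therapy stop time" lies beyond the same hour 24. PPCflg3 (pneumonia) and PPCflg4 (ICU readmission or transfer to a higher level of care) have no hour-24 threshold. Death is not a component.

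**Stop time.** The definition is "IMV Stop Time=date & time of the earlier of stop of IMV or PSHA+7". The only missing-data rule for a stop covers a known date with an unknown clock time: "then the IMV stop time will be taken as the assessment time". Death is not named as a stop, and nothing covers a stop that was never recorded.

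**Secondary endpoints.** The >48 h endpoints are derived by similar logic. Hospital stay runs to discharge, and total ventilation time runs to discharge from the initial stay (SAP 2.2). For ICU stay, hospital stay, time on ventilation and time to extubation, SAP 6.3 says "Mean, median, and standard deviation will be presented for the following endpoints". The one special case for extubation is extubation before hospital admission: "then time to initial extubation will be set to zero". That rule does not concern death, and a patient who is never extubated has no rule.

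**Deaths.** Mortality appears only in the protocol's background. It is not an endpoint in either document and not among the five daily milestones in Protocol 3.4.1. SAP 6.1.2 counts subjects enrolled. SAP 6.4 covers device effects and complaints in Stage II only.

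**The concern.** Flags 1 and 2 depend on how late support ended. Death ends support, so a very bad outcome can receive the value meant for a good one. The duration endpoints have the same weakness: dying early gives a short stay and few ventilator hours, which a plain mean or median treats as favourable.

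The gap is more than missing detail. Followed literally, the text allows two opposite codings of the same patient, and the more natural one ranks a death above a survival. If early mortality differed between stages, the reported rates and durations would move for a reason unrelated to pulmonary complications, and a reader would have no count of deaths with which to notice it.

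**Working it through.** The plan states no mortality rate, effect size or power, so there is no figure of its own to reproduce. The check applies the flag rule to test patients and then sizes one miscoded death.

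**1. Flag rule.** With hours counted from PSHA, stop = min(end of invasive ventilation, 168) and PPCflg1 = 1 if stop > 24. The >48 h endpoint uses 48 in place of 24.

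| Patient | Stop (h) | PPCflg1 | >48 h |
|---|---|---|---|
| Dies ventilated at hour 20, death taken as stop | 20 | 0 | 0 |
| Dies ventilated at hour 20, no stop recorded, cap applied | 168 | 1 | 1 |
| Survivor extubated at hour 26 | 26 | 1 | 0 |
| Dies ventilated at hour 30, death taken as stop | 30 | 1 | 0 |

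Rows 1 and 2 are the same patient. Rows 1 and 3 show the reversed ranking. Row 4 shows that the primary flag catches a death on support after hour 24, but the >48 h endpoint does not.

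**2. Size on the primary endpoint.** Inputs: 200 patients per stage (Protocol Synopsis) and an expected PPC rate of 5% to 15% (Protocol 3.5.1).
- One unflagged death: 1/200 = 0.5 percentage points of that stage's rate.
- Expected PPCs per stage: 200 × 0.05 = 10 to 200 × 0.15 = 30, so one death is 1/30 to 1/10 of the event count.
- 95% half-width for one stage, 1.96 × √(p(1−p)/200): 3.0 points at 5%, 4.2 at 10%, 4.95 at 15%. For a difference between two stages with equal rates, multiply by √2: about 4.3 to 7.0 points.

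**3. Direction.** Assume the true risk of PPC or death is equal in the two stages and that no early death was flagged in another way. The false difference (Stage I minus Stage II) is then (deaths in II − deaths in I)/200. The death counts below are assumptions.

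| Early deaths, I vs II | False difference | Counting PPC or death |
|---|---|---|
| 1 vs 1, or 2 vs 2 | 0.0 points | 0.0 |
| 1 vs 3 | 1.0 point towards the device | 0.0 |
| 2 vs 6, or 0 vs 4 | 2.0 points towards the device | 0.0 |
| 4 vs 0 | 2.0 points against the device | 0.0 |

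**4. Size on mean hospital stay.** With d early deaths at 0.8 day and a survivor mean of L days (both assumed), the mean falls by d × (L − 0.8)/200. The smallest case, d = 1 and L = 6, gives 5.2/200 = 0.03 day. The largest, d = 6 and L = 10, gives 6 × 9.2/200 = 0.28 day.

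**The case against.** A reader might infer that the SAP scores every death before hour 24 as 'no PPC', so that early mortality reads as a benefit of the device. The documents do not support that, for three reasons.

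- The SAP never says that death is a stop time. With no recorded stop and the cap applied, the result is the opposite, and flags 3 and 4 can be met before an early death.
- Flags 1 and 2 miss only deaths on support before hour 24. Later deaths on qualifying support are counted.
- Equal early mortality lowers both rates and cancels in the comparison, and more deaths in Stage I work against the device. The Stage II filters do not settle the direction. SAP 6.2 removes Stage II patients who never received the device, including any who died first, while comparable Stage I deaths stay in and may score 'no PPC'. That works against the device. The rule that Stage II events must follow device use works the other way.

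A reader might also say that the SAP abandoned a commitment to survival methods for these durations. The Protocol Synopsis does say that time-to-event data "will be summarized with methods appropriate for survival data including a Kaplan-Meier plot", but its only example is time to readmission. For stay and ventilation time, Protocol 3.5.2 plans descriptive summaries, and the SAP follows it. The planned median is also little affected by a few deaths.

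Deaths would not be wholly invisible either. Serious adverse device effects are listed for Stage II, follow-up time is summarised, data listings are promised, and discharge location is collected. None of these is a count of deaths by stage.

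These objections limit size and direction. They leave standing the missing rule, the reversed ranking on the natural reading, and the lack of any death count.

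**Conclusion.** The point holds as an undefined rule with a perverse result on its most natural reading. A death on the ventilator before hour 24 scores 0 on flags 1 and 2, where a survivor extubated at hour 26 scores 1. The >48 h endpoints and the durations share the weakness, and no planned table shows deaths in either stage.

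The size is 0.5 points per unflagged early death. A surplus of four in one stage gives 2.0 points, which is below the uncertainty of the comparison but not negligible beside a 5% to 15% rate. Mean stay moves by about 0.03 to 0.28 day for one to six early deaths. These results rest on assumed death counts, times of death and survivor stays, because the documents give no mortality figure. A bias in favour of the device is possible but not shown: it requires more unflagged early deaths in Stage II than in Stage I.

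**What to change.** Treat this as a cheap improvement and leave the primary endpoint unchanged.

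1. In SAP 6.1.1, state how the stop time of each form of support is set when the patient dies, and what applies when no stop is recorded.
2. Tabulate deaths by PSHA+7 and deaths in hospital, by stage.
3. Pre-specify a sensitivity analysis of PPC or death by PSHA+7.
4. Alongside the planned summaries of stay, ventilation time and time to extubation, report the cumulative incidence of discharge alive and of extubation, with death as a competing event.

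The cost is SAP text, a few tables, and abstraction of vital status and time of death from charts already under review. Protocol 3.4.1 already collects the date, time and destination at discharge. Stage I data are gathered before Stage II starts, so Stage I charts may have to be reopened if the case report form does not already record death.
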